## 8.2 Exclusion criteria

Children will not be eligible for inclusion if they **have**:

- Used oral or topical antibiotics to treat a skin infection within the past week.
- Have used potent or very potent topical corticosteroids (Appendix IV) within the past two days.
- Treating clinician believes the patient has a severe infection requiring immediate antibiotics or is arranging immediate hospitalisation or urgent (same or next day) dermatology referral because of the severity of the eczema or suspected infection.
- Features suggestive of eczema herpeticum (significant pain, punched out lesions).
- Known significant comorbid illness (e.g. significant immune compromise)
- Allergy to fusidic acid or both penicillin and erythromycin.
- Contraindication to any study medication (penicillin, erythromycin, fusidic acid).

Or if they **do not have**:

- A parent or legal guardian who is able to provide written informed consent.
- A parent/legal guardian (or a person delegated by the parent/legal guardian) who expects to be available for follow-up visits at 2, and 4 weeks and who understands English well enough to complete simple verbal and written questionnaires.

## 9 Recruitment of participants

### 9.1 Number of participants

A total of 516 participants will be required.

### 9.2 Recruitment procedure

Participating clinicians will be asked to sequentially identify suitable children during routine consultations. Some clinicians will be aided in the identification of suitable children through the use of a software package – Trial Torrent software (see 9.2.5.1 below).

#### 9.2.1 Informing parents of potentially eligible children about the trial

Following set up of general practice sites and dermatology units, we will ask the site to identify all children less than 8 years of age who have a history of eczema recorded in their electronic medical record and to write to their parent/legal guardian(s) (herein referred to as parent/carer(s)) to inform them about the

study. The purpose of this letter is to provide parent/carer(s) with advanced notification and information about the study; including the potential risks and benefits of taking part, in order to facilitate their decision about participation should their child develop a possible infection during the course of the study.

### **9.2.2 Identification of potentially eligible children**

Potentially eligible children will be identified by clinicians at the time of consulting. The clinician will explain the study to the child's parent/carer(s), and provide them with a written participant information sheet (PIS).

### **9.2.3 Parent/carer(s) is interested in their child taking part**

The clinician will ask interested parent/carer(s) for verbal consent to pass to the research team, i) contact details and ii) details of the child's current illness and penicillin allergy status.

Clinicians will record examination findings, working diagnosis, current treatment and penicillin allergy status on a paper log or electronic case report form (CRF) depending on whether the practice is using the Trial Torrent software or not (see section 9.2.5 below). This data will be used to help assess eligibility and need for non-penicillin treatment.

The clinician will also prescribe corticosteroid cream(s) or ointment(s) for all children (Eumovate for trunk and limbs and/or 1% hydrocortisone for face), emollients if the parents do not already have a supply sufficient for at least two weeks (the choice of emollient to be decided by the clinician in conjunction with the parent/carer(s), however emollients containing antimicrobial agents must not be used) and give advice on optimal care of eczema (including an information leaflet).

Finally, the clinician will complete a study prescription for study medication on a triplicate form. One copy of this form will be kept by the general practice, and will be used to fax a copy to the study pharmacy. The clinician will provide the parent/carer(s) with a trial information folder containing the original and a copy of the prescription. When the research nurse meets the parent/carer(s) at the baseline appointment, the research nurse will collect the original and copy of the prescription from the parent/carer(s). The research nurse will keep the copy, and deliver the original prescription to the study pharmacy.

### **9.2.4 Parent/carer(s) is not interested in their child taking part**

If the parent/carer(s) is not interested in participating at this point the study team will not contact them. Clinicians will be asked to keep a log of non-

identifiable information, including the reasons for non-consent (where given by the parent/carer(s)), for all eligible children who are not recruited into the study. These data will be used to assess for selection bias. The clinician will continue to treat the child according to their usual practice.

## **9.2.5 Use and evaluation of the recruitment software**

### **9.2.5.1 *Trial Torrent software***

We plan on using the Trial Torrent software package (formerly known as Scottish Acute Recruitment Multi-Agent (SARMA))  to aid in the identification of suitable patients and notification of the research team that a suitable participant is interested. All practices will be encouraged to have this package installed on their practice computers, but use of the software will not be a requirement of participation. In order to evaluate its effectiveness as a tool to aid recruitment (see Section 9.2.5.2), Trial Torrent will only be activated as a prompt for clinicians in some practices. For the evaluation, practices will be randomised based on a randomisation schedule.

Trial Torrent sits on the practice's computers and links with their clinical software system in order to identify when pre-programmed Read codes (codes used in general practice computer systems to identify symptoms, diagnoses, or medications) are used by the clinician. In practices randomised to use of the recruitment software a pop-up box will notify the clinician that the patient may be eligible for inclusion. This box can be used to indicate whether the patient has been given additional information, and if so, whether the patient's parent/legal guardian has verbally consented to have their information transmitted to the research team. In addition, for those who agree to a visit from the research nurse, the software can be used to record additional information (such as clinical features) and send these along with patient contact details and penicillin allergy status directly to the research team using a secure website, email and/or SMS messaging.

This software has been developed in conjunction with the major manufacturers of general practice clinical software systems in the UK, and has been previously used in a UK primary care study. The system integrates with the practice electronic health record (EHR) system using an approach that is carefully designed to minimise load on the host system. Consequently, there should be no noticeable effect on performance. The system is also secure and will only transmit data that patients (or their parent/carer) have consented to pass on.

In the remaining practices, although pop-up prompts will not appear, clinicians will have the option of using the Trial Torrent software to pass clinical and contact

details to the nurse. Furthermore, clinicians who do not have Trial Torrent installed and those randomised to not have Trial Torrent prompts, can choose to send patient details via a web portal (Stand-Alone Trial Torrent (SATT)) or by fax.

Clinicians who fax will be asked to fax a referral form to a secure fax machine in the research centre to indicate that a potential participant has been identified. The research centre will contact the research nurse via SATT.

If at the baseline visit a patient's parent/carer(s) does not fully consent to participating in the study, data held in relation to the referral, on electronic devices, such as mobile phones and Trial Torrent servers will be deleted and/or anonymised as required by a CREAM-specific standard operating protocol.

#### **9.2.5.2 *Evaluation of the Trial Torrent software***

We have been asked by our research funders to evaluate use of this recruitment aid. In order to do this we will conduct a nested evaluation. GP Practices that are willing to use Trial Torrent will be randomly assigned to receive Trial Torrent prompts or not. Randomisation will occur at the time of practice enrolment and will be minimised by list size (less than 6,000, greater than 6,000) and whether the practice is research active or not in the past 12 months.

At three and six months (from the start of patient recruitment) we will compare the **mean recruitment rate** (recruited patients per month recruiting per whole time equivalent (WTE) participating clinician) for GP practices in each arm (of the Trial Torrent evaluation). In addition, at three months from the start of recruitment the Trial Statistician will compare the **time to first patient recruited** in the two groups and present analysis to the TMG. If we find a significant improvement in either the mean recruitment rate or time to first patient recruited at three months or in mean recruitment rate at six months then the evaluation will be stopped and the Trial Torrent software will be rolled-out to the rest of the practices. If no significant improvement is found at either of these time points then we will continue the evaluation until the end of the recruitment period (12 months) and compare the mean recruitment rate in the two arms at this time. Since the analysis of the mean recruitment rate at 3 and 6 months are interim analyses the significance level for those tests needs to be adjusted if we are to retain an overall significance level of 5%. The Pocock method will be used implying a significance level of 0.022 will be used for all three analyses . This will facilitate the early stopping of the sub-study if it is found to improve recruitment. With 90 practices we would have a power of 84% for detecting a

hazard ratio of 0.5 with an estimated standard deviation of 0.5 and at the 2.2% significance level.

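### The 84% power stated for the Trial Torrent evaluation needs a first recruit in all 90 practices; at the 3-month test, even recruitment would give about 66 and a power of about 70%

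*Protocol*

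**What the plan says.** Protocol section 9.2.5.2 randomises general practices to receive software prompts or not, and gives this power statement: "With 90 practices we would have a power of 84% for detecting a". The effect size, spread and level come in the rest of that sentence: "hazard ratio of 0.5 with an estimated standard deviation of 0.5 and at the 2.2% significance level". It names neither an outcome nor a time of analysis.

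The section plans two outcomes:

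- **Mean recruitment rate**, compared at 3 months, at 6 months and, if the evaluation is still running, at the end of recruitment. On the level: "The Pocock method will be used implying a significance level of 0.022 will be used for all three analyses".
- **Time to first patient recruited**, compared once: "at three months from the start of recruitment the Trial Statistician will compare the" two arms on this outcome. No later comparison of it is planned.

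A significant improvement at 3 months (either outcome) or at 6 months (mean rate) stops the evaluation and the software is rolled out. Otherwise "we will continue the evaluation until the end of the recruitment period (12 months"), with a final comparison of mean rates. On the size of the main trial, section 9.1 says: "A total of 516 participants will be required".

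The section does not give the number of practices expected to have recruited by 3 months.

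**The concern.** Power to detect a hazard ratio depends on the number of events, not on the number of units randomised. Here an event is a practice recruiting its first child. A practice with no recruit when the data are analysed is censored and adds little information.

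The power sentence gives the number of practices and a hazard ratio but no event count. If the calculation counted every practice as an event, it describes a test with complete follow-up, whereas the planned test comes a quarter of the way through a 12-month recruitment period. The 84% would then overstate the power of the only test that uses a hazard ratio. Someone reading a non-significant time-to-first-patient result beside the stated 84% would give it more weight than it deserves.

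**Working it through.** **Inputs**

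- From section 9.2.5.2: 90 practices, taken as 45 per arm; hazard ratio 0.5; standard deviation 0.5; level 0.022; time to first recruit tested at 3 months; recruitment period 12 months.
- From section 9.1: 516 participants.
- Assumed, because the protocol does not say: a two-sided test, constant recruitment rates, all 90 practices open from the start, and the share of the 516 children who come from these practices.

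**Step 1. Reproduce the 84%.** For a log-rank or Cox comparison with 1:1 allocation (Schoenfeld):

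power = Φ(0.5 × |ln HR| × √events − z), with z = 2.290 for two-sided 0.022.

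The factor 0.5 is the standard deviation of a 1:1 arm indicator, √(0.5 × 0.5), which matches the value in the protocol.

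With 90 events: 0.5 × 0.693 × √90 = 3.288; 3.288 − 2.290 = 0.998; power = 84.1%. Solving the other way, 84% power needs 90 events.

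Other readings do not give 84%:

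| Reading | Power |
|---|---|
| One-sided 0.022, 90 events | 89.9% |
| Two-sided 0.05, 90 events | 90.8% |
| Freedman's formula, 90 events | 80.8% |
| Two means, difference 0.5, SD 0.5, 45 per arm | 99.3% |

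So the stated figure corresponds to 90 events from 90 practices, with no censoring.

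**Step 2. Events expected by 3 months if all 516 children come from these practices.**

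- Average rate: 516 / (90 × 12) = 0.478 children per practice per month.
- Split 1:2 between arms, keeping the total at 516: 0.478 × 2/3 = 0.319 and 0.478 × 4/3 = 0.637 per month.
- Share of practices with a first recruit by 3 months, 1 − exp(−3 × rate): about 62% and 85%.
- Events: 27.7 + 38.3 = 66.

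**Step 3. Power with 66 events.** 0.5 × 0.693 × √66 = 2.816; 2.816 − 2.290 = 0.525; power = 70%. A simulated log-rank test under the same assumptions gives 69%.

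**Step 4. Vary the assumptions.**

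| Assumption | Events by 3 months | Power, HR 0.5 |
|---|---|---|
| All 516 from these practices | 66 | 70% |
| Three quarters of them | 57 | 63% |
| Half of them | 45 | 51% |
| All 516, but practices open evenly over the 3 months | 41 | 47% |
| Average rate of 0.478 used for both arms when counting events | 69 | 72% |
| Control arm at 0.478, prompted arm at double | 77 | 77% |

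The last row implies 45 × 12 × (0.478 + 0.956) = 774 recruits in a year, more than the 516 planned. Shares below one are plausible because section 3.1 places the trial in secondary care as well as primary care, and section 9.2.5.1 makes use of the software optional.

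**Step 5. When 84% would be reached.** On the Step 2 rates, about 82 practices would have recruited by 6 months (80% power) and 89 by 12 months (84%). The protocol plans no test of time to first recruit at either point.

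**The case against.** The strongest reply is that the arithmetic is correct as it stands and that the rest is inference. The sentence does not name its outcome, does not say that all practices will have recruited, and gives no rate per practice. This is true. The link to time to first patient rests on two facts: nothing else in the section has a hazard ratio, and 84% appears only with 90 events. The 70% is likewise conditional. The protocol does not say that recruitment is even, and the advance letters to parents (section 9.2.1) could bring recruits in earlier. The event counts must therefore be presented as assumptions.

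A reader might go further and infer that the evaluation as a whole lacks 84% power, or that a null result at 3 months would be taken as evidence against the software. The documents support neither.

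- A non-significant result at 3 months leads to continuation, not to a conclusion.
- Mean recruitment rate is tested up to three times. Simulating those three tests alone (two-fold difference, Welch test on practice counts at the 2.2% level, staffing adjustment ignored) gives at least one success in about 88% to 100% of runs with no or moderate between-practice variation (gamma variance 0 or 0.5). It falls to about 69% to 75% only when that variance is set at 1.0.

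It is also tempting to quote the lower power for time to first recruit that such variation produces, about 44% and 30% for variances of 0.5 and 1.0. The documents give no figure for that variation. It also pulls the marginal hazard ratio towards 1, so those runs no longer test a hazard ratio of 0.5. They are not relied on here.

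The absence of a separate power statement for mean recruitment rate is missing detail, not an error.

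**Conclusion.** The point holds for one test. The 84% is the power of a comparison in which all 90 practices have recruited, and the protocol schedules its only time-to-first-patient comparison at 3 months, when on its own recruitment target many would not have done so. With constant rates, all practices open from the start and all 516 children coming evenly from these practices, power for a hazard ratio of 0.5 is about 70% (66 events). With half the children from them it is 51% (45 events). The chance of missing a true hazard ratio of 0.5 at that test is then about 30% to 49%, not 16%.

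Severity is minor to moderate. Only a nested study of a recruitment aid is affected. The sample size of the main trial and its treatment comparisons are untouched.

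**What to change.** Restate the last sentence of section 9.2.5.2 so that it says three things:

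1. The 84% refers to time to first patient recruited, for a hazard ratio of 0.5 at the two-sided 2.2% level, and requires 90 practices to have recruited a first patient.
2. For the planned 3-month comparison, power for the same hazard ratio is about 70% with 66 practices having recruited and about 51% with 45.
3. The counts of 66 and 45 are assumptions, derived from 516 children recruited evenly over 12 months with all, or half, of them coming from these practices and all practices open from the start.

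If the study team has a better forecast of first recruits by 3 months, it should use that in place of these counts in the formula under Step 1.

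The cost is one reworded sentence and a less favourable stated figure. The design, the number of practices and the stopping rule need not change.

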### **9.3 Informed Consent**

The research nurse will contact parent/carer(s) (within 48 hours) who have agreed to have their contact details passed to the research team, and arrange to visit them at their home or another mutually acceptable location within 72 hours (usually 48 hours) of their clinic consultation. During the visit the nurse will discuss study participation in detail, check eligibility, answer questions and check understanding, and ask parents to provide informed consent for their child's participation. The parent/carer(s) will be given as much time as they require for reading the study materials and for asking questions.

Consent will be taken by a research nurse who will have been trained in taking informed written consent. At least one parent or legal guardian must provide informed consent in order for the child to be enrolled in the study.

We will comply with Welsh language requirements and the PIS, Consent Form and any other required participant documentation will be available in Welsh. However, all documentation used for data collection (i.e. outcome measures) will remain in English as they are designed and validated in English.

### **9.4 Randomisation, blinding and unblinding**

Randomisations lists will be prepared by the study statistician. Each Site Pharmacy will be provided with two randomisation lists, one for patients not allergic to penicillin and one for those who are. These will be block randomised with randomly chosen balanced blocks of six or nine. As patients are recruited they are assigned the next vacant Participant Identification number (PID). The randomisation list will link each unique PID to a treatment group, denoted A, C or E for the non-penicillin allergic group; and B, D and F for the penicillin allergic group. The pharmacist will then select a treatment pack(s) for the relevant treatment arm based on a trial pack randomisation list. This is to ensure that trial pack identification numbers cannot be used to identify treatment allocation. The Trial Pack contains the prescribed medication as detailed in Section 11.3. The process is described in more detail in the Trial Pack Randomisation Protocol.

At the point when a research nurse arranges to visit a potential participant, they will inform their local Site Pharmacy who will begin preparing a Trial Pack based on the faxed prescription received from the clinician and the randomisation list.

Therefore, site pharmacists will not be blinded, but the research nurses will remain blinded at all times.

The research nurse will collect the Trial Pack(s) from the Site Pharmacy and transport the Trial Pack to the patient's home. The research nurse will only release Trial Pack(s) once informed consent has been obtained and a Consent Form signed. Participant randomisation will be considered to have occurred once a Consent Form has been signed and the Trial Pack opened. The Trial Pack number will then have been entered onto the participant's CRF. If consent is not obtained then the Trial Pack will be returned to the study pharmacy, logged and destroyed. Further details for IMP destruction will be provided to the research nurse and site pharmacies in a trial-specific IMP management standard operating protocol.

#### **9.4.1 Blinding**

Clinicians at sites and research nurses will remain blinded throughout the study, unless they are providing clinical treatment to a serious adverse event, in which case they can contact the research centre for unblinding.

Site pharmacists will not be blinded as they are required to randomise, prepare and dispense the correct Trial Pack(s).

#### **9.4.2 Unblinding**

The treatments used in this study are all licensed products (or their placebos) used within their licensed indications, and the participants will be provided with information about the medication they may be on (i.e. Flucloxacillin, or its placebo; erythromycin, or its placebo; fusidic acid, or its placebo). The most likely adverse event that may necessitate unblinding is a possible allergic reaction to study medication. Furthermore, if a serious adverse event (SAE) (Section 12) occurs or unblinding is required for any reason, we will provide a 24 hours a day unblinding service.

Research nurses will advise parent/carer(s) to contact NHS Direct, their primary care out-of-hours provider, or the emergency ambulance service if the participant should require out-of-hours medical attention. The parent/carer(s) will be advised to ensure they provide the participant's Trial Pack, Patient Information Leaflet (PIL) and other trial documentations to the treating clinician(s). This information will notify the treating clinician(s) that the participant is either taking flucloxacillin suspension or erythromycin suspension orally, or their placebos, or applying fusidic cream or its placebo.

All Trial Packs will contain a PIL for each study medication, and all participants provided a PIS by the research nurse which will include information on unblinding. In the event that a clinician treating a study participant feels the need to know the study medication that a participant is taking (or has taken), they can request unblinding of that participant's study medication by telephoning the number below 24 hours a day. Randomisation lists will be kept in a secure location that is accessible to staff providing the unblinding service.

**Contact SEWTU for unblinding:  
[contact]**

